7.1 Number of Patients

A total of approximately 108 patients are planned to be randomized into the trial; approximately 72 to the glepaglutide treatment groups (36 in each of the 2 active treatment groups) and approximately 36 to the placebo treatment group, after the PS Stabilization Phase is completed. A screen failure rate of 15% is expected, hence, approximately 152 patients may need to be screened.

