7.2. ADVERSE EVENTS

Adverse events (AEs) will be coded using MedDRA V24.1. All treatment-emergent AEs (TEAEs) from the start of trial drug dosing will be collected.

Treatment-emergent AEs are defined as AEs with onset date on or after the first day of exposure to investigational product. Unless otherwise stated, all outputs will be presented for treatment-emergent AEs and, for simplicity, referred to as AEs.

Related AEs are defined as events classified as 'possibly related' or 'probably related' by the investigator.

Severity categories will include mild, moderate, and severe. Any missing severity will be imputed as severe prior to selecting the report that will contribute to the summary. As a result, a patient would be counted as severe due to a missing severity, even if the patient reported similar events at a lesser degree of severity. The same logic will be applied to the related AEs.

For patients who permanently discontinued treatment due to an AE and who also withdrawal trial prematurely, the AE leading to treatment discontinuation is counted as an AE leading to trial withdrawal (regardless of the cause marked as leading to trial withdrawal).

Common AEs are defined as events (preferred terms) occurring in \geq 5% of patients in the glepaglutide 10 mg OW or glepaglutide 10 mg TW treatment groups.

For all AE tables summarized by SOC and PT, a patient contributes only once to the count for a given AE on the SOC level and on the PT level within SOC. AE incidence tables will be sorted by descending frequency counts in hierarchical order of glepaglutide 10 mg twice weekly, then by glepaglutide 10 mg once weekly, and then by placebo. PTs will be sorted in similar hierarchical fashion within the SOC.

If there are less than 5 AEs of a type (AEs leading to treatment discontinuation, AEs leading to trial withdrawal, AESIs or AEs in other safety areas of interest) in the entire observation period, then only a listing will be prepared.

The following AE summaries will be presented by treatment group and will present the following information:

- n: number of patients experiencing at least one AE
- %: percentage of patients experiencing at least one AE
- E: number of AEs
- R: event rate (calculated as the number of AEs divided by PYO multiplied by 100)

An overall summary table will include the number and percentage of

- All adverse events
- Serious adverse events

25 August 2022

- Severity (Mild, Moderate, Severe, Missing)

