- Relationship (Possibly, Probably, Unlikely, Not Related, Missing)
- AEs leading to trial withdrawal
- AEs leading to treatment discontinuation
- AEs leading to treatment pause
- Outcome (Recovered/Resolved, Recovering/Resolving, Recovered/Resolved with Sequelae, Not Recovered/Not Resolved, Fatal, Unknown, Missing)

Additional AE tables will include:

- AEs by System Organ Class (SOC) and Preferred Term (PT)
- AEs Occurring in >=5% of Patients Treated with Glepaglutide by SOC and PT
- Summary of Serious AEs
- Serious AEs by SOC and PT
- Related AEs by SOC and PT
- Severe AEs by SOC and PT
- Moderate AEs by SOC and PT
- Mild AEs by SOC and PT
- AEs of Special Interest (AESIs) by Type and PT
- Other safety areas of interest (see Table 8) by SOC and PT

Other safety areas of interest are defined based on:

- their relevance for the SBS population or known class effects with other glucagon-like peptide-2 (GLP-2) receptor agonists (RAs) (e.g. gastrointestinal stenosis and intestinal obstruction [including stoma complications]; fluid retention and volume overload; hepatic disorders)
- general applicability to injectable peptide drugs (e.g. injection site reactions; hypersensitivity reactions)
- general interest for any new drug administered long-term (e.g. rare events; adverse event by organ system or syndrome [e.g., cardiac, renal and hepatic events]).

For these other safety areas of interest, events will be captured by applying the MedDRA queries as defined in Table 8. Both overall summary tables and tables by PT will be presented by treatment group for each safety area of interest separately. The following plots will be presented for injection site reactions and abdominal pain:

• Survival probability function plots (one minus the Kaplan-Meier estimator) for the time to the first occurrence of the selected AEs will be presented. Time to the first AE will be calculated from the date of first dose of investigational product.

• Mean cumulative function plots to evaluate recurrent AEs occurring after the date of the first dose of investigational product, showing the mean number of events over time.

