The risk difference with 95% confidence intervals (using the Miettinen and Nurminen estimation method) will be estimated to quantify the uncertainty of the treatment comparison between placebo and glepaglutide 10 mg OW, placebo and glepaglutide 10 mg TW, and placebo and either of the glepaglutide groups (glepaglutide total); no formal hypothesis testing will be performed. This comparative analysis will be done for AEs leading to treatment discontinuation, AEs leading to trial withdrawal, SAEs, prespecified AESIs, other safety areas of interest and AEs occurring in \geq =5% of patients treated with glepaglutide (10 mg once weekly or 10 mg twice)

weekly). The result will be presented graphically with a dot plot in the left panel illustrating the event rates by treatment group (e.g., glepaglutide 10 mg once weekly and placebo) and a forest plot in the right panel presenting the corresponding risk difference and confidence intervals.

As a separate table, Symptoms of Injection Site Reactions will be presented with patient counts, percentages, number of events, and adverse event rate for injection site reactions including spontaneous pain, pain on palpitation, itching, redness, oedema, induration/infiltration, and other. The above symptoms are captured for AEs with a Tick mark for 'study treatment injection site reaction' in the eCRF (AE form).

The following patient listings will be provided as tables:

- Deaths
- Serious AEs
- AEs Leading to Trial Withdrawal
- AEs Leading to Treatment Discontinuation
- AEs Leading to Treatment Pause
- AESIs
- AESIs Details on Neoplasms
- Other Important Events

A listing of all TEAEs will be provided.

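### The SAP picks common adverse events for the risk-difference plot on glepaglutide frequency alone, so low-frequency terms lean slightly towards harm and terms common only on placebo get no interval

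*SAP*

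**What the plan says.** SAP 7.2 applies the 5% rule in three places.

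- The definition of common AEs covers preferred terms reaching at least "5% of patients in the glepaglutide 10 mg OW or glepaglutide 10 mg TW treatment groups".
- The list of additional tables includes "AEs Occurring in >=5% of Patients Treated with Glepaglutide by SOC and PT".
- The risk-difference analysis (Miettinen-Nurminen 95% intervals; placebo against once weekly, twice weekly and both combined) takes its common events from those reaching at least "5% of patients treated with glepaglutide (10 mg once weekly or 10 mg twice" weekly).

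None of the three mentions a placebo frequency. The version history in SAP section 9 records that the definition was added in version 6.0 for ease of reference, and gives no reason for leaving placebo out.

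Other parts of the same section limit what the rule can do. "This comparative analysis will be done for AEs leading to treatment discontinuation, AEs leading to trial withdrawal, SAEs, prespecified AESIs, other safety areas of interest" as well as for common events, and those other groups carry no glepaglutide percentage. "The following AE summaries will be presented by treatment group", and the tables include an unthresholded one, "AEs by System Organ Class (SOC) and Preferred Term (PT"). For the risk differences, "no formal hypothesis testing will be performed".

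**The concern.** Visits and adverse event recording are the same in all arms, but admission to the common-event comparison is not. The active side has two chances to bring a term in and placebo has none. There are two consequences.

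1. **Selection.** When a term has the same true risk everywhere, it is more likely to be plotted if a glepaglutide count happened to be high. The plotted differences for low-frequency terms are then shifted upwards on average, and the intervals take no account of this.
2. **Omission.** When a non-serious term is really less frequent on glepaglutide, the larger the reduction, the less likely the term is to receive an estimate.

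At stake is how fairly one display can be read. SAP 7.2 says the risk differences are there to convey the uncertainty of the treatment comparison, and for terms close to the cut they do so with a small built-in tilt.

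**Working it through.** **Plan's own figure.** The documents give no adverse event rates and no calculation on this point, so there is nothing to reproduce. The true risks below are assumptions, shown over a range.

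**Inputs.** Arm size: Protocol 7.1 plans about "36 in each of the 2 active treatment groups" and about 36 on placebo. Threshold: 0.05 × 36 = 1.8, so a term qualifies at 2 patients. SAP 2.6 allows 33 to 37 per arm; 0.05 × 33 = 1.65 and 0.05 × 37 = 1.85, so the threshold is 2 patients throughout.

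**Model.** Independent binomial counts, n = 36 per arm, true risk p in every arm.

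- Probability that one arm misses the cut: q = (1−p)^36 + 36p(1−p)^35.
- Probability that the SAP rule shows the term: 1 − q², because either glepaglutide arm suffices. As the arms are independent, q² is also the share of terms reaching 5% on placebo that are not shown.
- Expected count in a given glepaglutide arm, if shown: E = [36p − q × 36p(1−p)^35] / (1 − q²).
- Expected displayed difference from placebo: E/36 − p. The placebo count is unaffected by the selection. The result is the same for either glepaglutide arm and for the two combined.

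**Worked case, p = 3%.** (0.97)^36 = 0.334 and 36 × 0.03 × (0.97)^35 = 0.372, so q = 0.706 and q² = 0.498. P(shown) = 0.502. E = (1.08 − 0.706 × 0.372)/0.502 = 1.63. The difference is 1.63/36 − 0.03 = 0.0453 − 0.03 = +1.5 points.

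| True risk, all arms | P(shown) | Placebo-common terms not shown (q²) | Expected displayed difference, points |
|---|---|---|---|
| 1% | 0.098 | 90% | +2.4 |
| 2% | 0.297 | 70% | +2.0 |
| 3% | 0.502 | 50% | +1.5 |
| 5% | 0.791 | 21% | +0.8 |
| 8% | 0.958 | 4% | +0.3 |
| 10% | 0.987 | 1% | +0.1 |

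Under a rule that admits a term reaching 5% in any of the three arms, the expected difference is 0 by symmetry.

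**A real reduction.** Take 10% on placebo and 2% on each glepaglutide arm. At 2%, q = 0.838, so the term is omitted with probability 0.838² = 0.70. At 3% on each glepaglutide arm, omission is 0.706² = 0.50.

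**Scale against the intervals.** For both glepaglutide arms combined (72) against placebo (36), the approximate half-width is 1.96 × √[p(1−p)(1/72 + 1/36)]. This is 6.8 points at 3% and 8.7 points at 5%, against shifts of 1.5 and 0.8.

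**Pooled reading.** The table title and the risk-difference sentence could be read as 5% of all glepaglutide patients: 0.05 × 72 = 3.6, so 4 of 72. Conditioning a binomial count with n = 72 on being at least 4 gives a shift in the pooled difference of +4.0 points at 2%, +2.1 at 5% and +0.4 at 10%. The tilt is larger than under the per-arm definition.

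**The case against.** The strongest case is that little is lost. Four inferences that go too far should be set aside.

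- *Placebo-common terms are never compared.* The documents do not support this. The full table by system organ class and preferred term, and the tables by severity and relatedness, show every arm without a threshold. Only the computed difference and interval are missing.
- *The common-event plot is the only comparative display for non-serious harms.* It is not. The areas in SAP Table 8 include abdominal pain, injection site reactions, hypersensitivity, fluid retention, and hepatic and renal events. They are not limited to serious events and get risk differences without a glepaglutide percentage. A separate rule in SAP 7.2 reduces some groups to a listing when there are fewer than 5 events, but that rule does not depend on arm.
- *The rule hides the complications of parenteral support.* Protocol 4.1 names bloodstream infection, central vein thrombosis, liver damage and renal impairment. Hepatic and renal events are Table 8 areas. Life-threatening or hospitalised infection or thrombosis would be a serious event. Most would therefore enter by another route.
- *The tilt is 3 to 4 points.* That comes from looking at whichever glepaglutide arm is higher (+3.8 at 3%, +3.2 at 5%). With no threshold at all, the higher of two arms already exceeds placebo by 1.5 and 2.0 points on average. About 40% and 60% of those figures is thus unrelated to the rule, and the SAP plots no such contrast.

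It is also fair to say that selecting on the active arms contradicts nothing in either document, that the risk differences go beyond the descriptive summaries in Protocol 12.4, and that the tilt works against the sponsor's product. All this stands and keeps the point small. It does not make the selection symmetric.

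**Conclusion.** The point holds as a minor defect in one descriptive display. Selection into the common-event table and plot depends on the glepaglutide arms only. The resulting tilt towards harm matters for terms near 2 of 36 patients and is negligible from about 8 to 10% upwards. Even near the cut it is small beside the width of the intervals. The gap in coverage is limited to non-serious terms that are common only on placebo and fall outside the AESI, Table 8 and discontinuation or withdrawal groups.

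The sizes rest on 36 patients per arm, independent binomial counts and assumed true risks. No hypothesis test, type I error rate or efficacy result is affected. A reader might infer that the safety comparison as a whole is biased, or that glepaglutide harm is concealed. The documents support neither: the other risk differences are selected without this rule, and the lean is in the opposite direction.

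**What to change.** In SAP 7.2, define common AEs once, as preferred terms occurring in at least 5% of patients in any one of the three arms (twice weekly, once weekly or placebo), with the percentage judged separately in each arm. Use that one set in all three places: the definition, the common-event table and the risk-difference plot, and retitle the table to match. This also removes the possible pooled reading.

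Every term now shown stays, and terms reaching the cut only on placebo are added. The cost is one definition and a few more rows in one table and one figure. No new data are needed. If the current rule is kept, a footnote on the plot should at least say that terms were selected on glepaglutide frequency; that discloses the tilt but does not remove it.

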7.3. CLINICAL LABORATORY EVALUATIONS

Clinical laboratory parameters include:

Hematology:

Hemoglobin, Hematocrit, Red blood cell (RBC) count, White blood cell (WBC) count with differential (including absolute value and % value for neutrophils, lymphocytes, monocytes, basophils, and eosinophils), Platelet count, and International normalized ratio (INR)

Biochemistry:

Sodium, Potassium, Chloride, Bicarbonate, Blood urea nitrogen, Creatinine, Estimated creatinine clearance, Glucose, Calcium, Phosphorous, Magnesium, Alkaline Phosphatase, Alanine Aminotransferase (ALT), Aspartate Aminotransferase (AST), Gamma-glutamyl transferase (GGT), Lactic dehydrogenase, Conjugated bilirubin, Total bilirubin, Total protein, Triglycerides, Cholesterol, Albumin, Amylase, Uric acid, Zinc, and C-reactive protein (CRP)

Urine:

Blood, Glucose, Leukocytes, pH, Osmolality, Protein, Sodium, and Potassium

Confidential

Hematology, biochemistry, and pregnancy laboratory tests performed by a central laboratory will be included in ADLB dataset.

Due to the COVID-19 public health emergency, some of the trial participants were not able to come to the investigational site for all protocol-specified visits. Instead, the visits could be conducted as phone visits, if considered safe by the investigator. The investigator could also refer the patient to a local laboratory, if deemed necessary.

In general (independent of the COVID-19 pandemic), blood samples for analysis at a local laboratory can be drawn at the investigator's discretion during the trials; these values will be included in narratives for SAEs and AESIs as appropriate.

Descriptive statistics of the laboratory parameters will be presented by treatment group for all nominal trial visits at which they were collected. The change from baseline in hematology and biochemistry values will also be summarized by treatment group. Summary tables will also include the end of trial value defined as is the last available value in the trial and also the highest and lowest post-baseline values including values from unscheduled visits.Box plots of actual values will be produced for all hematology and biochemistry parameters. For laboratory parameters that are log-transformed the geometric mean will be presented in the box plot.

Values of aspartate aminotransferase (AST), alanine aminotransferase (ALT), alkaline phosphatase (ALP), total bilirubin (TB), gamma-glutamyl transferase (GGT), creatinine, blood urea nitrogen (BUN), estimated glomerular filtration rate (eGFR), and amylase will be log-transformed, and outputs will show the results back-transformed to the original scale. For these parameters, the geometric mean and coefficient of variation will be presented.

Hematology and biochemistry parameters will be presented as shifts from baseline (low, normal, high, missing) to each post-baseline visit where laboratory samples are scheduled for assessment.

Urinalysis parameters will be summarized as shifts from baseline (low, normal, high) to each visit assessed by treatment group.

For listings and plots of patient trajectories, all post-baseline central laboratory measurements, including unscheduled measurements will be included.

A listing of abnormal laboratory values will be presented.

Pregnancy laboratory tests will be listed only.

Separate figures by treatment group with individual patient trajectories over time of AST, will be presented for patients with at least one post-baseline AST value >3 times the upper limit of normal.. Similar plots will be presented for ALT, for patients with at least one post-baseline ALT value >3 times the upper limit of normal.

All central laboratory values will be included in patient data listings.

25 August 2022

Confidential

7.4. VITAL SIGNS

Vital signs data include measurements of heart rate (beats/minute), blood pressure (mmHg), and oral body temperature (Celsius). Descriptive statistics of the vital signs will be presented by treatment group for all nominal trial visits at which they were collected. The change from baseline will also be summarized by treatment group. Summary tables will also include the end of trial value defined as the last available value in the trial and also the highest and lowest postbaseline values including values from unscheduled visits.

Box plots of actual values should be produced for all vital sign parameters.

Shifts from baseline (Normal, Abnormal Not Clinically Significant, Abnormal Clinically Significant, Missing) to each post-baseline visit will be tabulated by treatment group for each vital sign parameter.

All vital signs data will be listed.

7.5. ECG

ECG parameters include heart rate (beats/min), PR interval (ms), PR interval Aggregate (ms), QRS duration aggregate (ms), QT interval aggregate (ms), QTcF interval aggregate (ms), and RR interval (ms), as well as the overall interpretation of each subject's ECG recorded as Normal, Abnormal Not Clinically Significant, or Abnormal Clinically Significant.

Descriptive statistics of ECG parameters will be presented for the actual values and change from baseline for each nominal trial visits by treatment group. Summary tables will also include the end of trial value defined as is the last available value in the trial and he highest and lowest postbaseline values including values from unscheduled visits.

Box plots of actual values should be produced for all ECG parameters.

Shifts from baseline in ECG overall interpretation to each scheduled post-baseline visit where ECG was assessed will be summarized by treatment group in tabular form.

Categorical summaries will present the number and percentage of patients with at least one postbaseline observation meeting the outlier criteria specified in Table 9. A listing with ECG parameter values will be provided for all patients with at least one post-baseline QTcF value >450 msec.

Parameter	Threshold
QTcF ^a	>450 ms
	>480 ms
	>500 ms
	Increase from Baseline in QTcF >30 ms

Table 9 Outlier thresholds for QTcF

Increase from Baseline in QTcF > 60 ms

Notes: a: based on threshold definitions in ICH E14, 2005. **Abbreviations**: QTcF: QT interval corrected using Fridericia's formula.

To support the outlier analyses for QTcF, AEs related to QT prolongation (defined by the MedDRA SMQ 'Torsade de Pointes/QT prolongation' [narrow scope]) will be summarized by preferred term.

All ECG data will be listed.

7.6. PHYSICAL EXAMINATION

A listing with physical examination findings will be provided.

7.7. IMMUNOGENICITY

7.7.1. Immunogenicity Assessment

A serum sample is defined as anti-drug antibody (ADA)-positive if results of the antiglepaglutide antibody screening and confirmatory assays are positive. If positive, a titer (highest dilution factor that still yields a positive reading) will be reported. Patients without any ADA data (evaluable samples) will be excluded from the analysis.

- 1. Pre-existing ADA (Yes/No) is defined, at the patient level, by the ADA status at trial baseline (i.e. Day 1), according to the presence or absence of ADA. This endpoint is defined for any patient with a valid ADA assessment at Day 1.
- 2. A treatment-boosted ADA positive patient (Yes/No) is defined, at the patient level, as any occurrence during the trial of at least a 4 fold increase from trial baseline in ADA-titer for patients with pre-existing ADA (and a titer at baseline).
- 3. A treatment-induced ADA positive patient (Yes/No) is defined, at the patient level, as any occurrence of ADA during the trial for patients without pre-existing ADA (based on a negative baseline ADA measurement).
- 4. An ADA positive patient (Yes/No) is defined by being either a treatment-boosted or treatment-induced ADA positive during the trial (for patients with a baseline ADA measurement).

Confirmed positive ADA samples will be further evaluated in three different ADA characterization assays: for in *vitro* glepaglutide neutralizing potential (NAb), for reactivity to the predominant metabolite (M2) and for cross-reactivity towards GLP-2. In case of a positive result in the ADA characterization assays, a titer will be estimated.

Confidential

For ADA negative samples, the missing assessments for in vitro glepaglutide neutralizing potential (NAb), for reactivity to the predominant metabolite (M2) and for cross-reactivity towards GLP-2 will be considered negative in all below analyses and presentations.

In case of positive results at study baseline (Day 1) in the ADA characterization assays ('Preexisting NAb', 'pre-existing M2 reactivity', 'pre-existing GLP-2 cross-reactivity'), the definitions and calculations for pre-existing ADA and treatment boosted ADA will correspondingly apply.

In case of a negative assessment in either of the four assays (ADA, NAb, M2 reactivity and GLP-2 cross-reactivity) the titer value will be set to ¹/₄ MRD (Minimal Required Dilution) for illustration purposes.

